10.2. Appendix 2: Clinical Laboratory Tests

- The tests detailed in [Table 4](#) will be performed by the local laboratory.
- Protocol-specific requirements for inclusion or exclusion of participants are detailed in [Section 5](#) of the protocol.
- Additional tests may be performed at any time during the study as determined necessary by the investigator or required by local regulations.

Table 4 Protocol-Required Safety Laboratory Assessments

Laboratory Assessments	Parameters			
Haematology	Platelet Count	RBC Indices: MCV MCH MCHC		WBC count with Differential: Neutrophils Lymphocytes Monocytes Eosinophils Basophils
	RBC Count			
	Haemoglobin			
	Haematocrit Reticulocyte % Reticulocytes			
Clinical Chemistry ¹	Urea	Potassium	Aspartate Aminotransferase (AST)/ Serum Glutamic-Oxaloacetic Transaminase (SGOT)	Total and direct bilirubin
	Creatinine	Sodium	Alanine Aminotransferase (ALT)/ Serum Glutamic-Pyruvic Transaminase (SGPT)	Total Protein Albumin
	Glucose ³	Calcium	Alkaline phosphatase	Lipids (fasted) ² : Total Cholesterol HDL LDL Triglycerides
	INR ⁴	APTT ⁴		
Routine Urinalysis	
 • Specific gravity • pH, glucose, protein, blood, ketones, by dipstick • Microscopic examination (if blood or protein is abnormal) 			

Laboratory Assessments	Parameters
Other Screening Tests	
 • Breath alcohol and urine drug screen (to include at minimum: amphetamines, barbiturates, cocaine, opiates, cannabinoids and benzodiazepines)] • Serology [(HIV antibody, hepatitis B surface antigen [HBsAg], hepatitis B core antibody [HBcAb], and HCV antibody) • QuantiFERON test for TB

NOTES :

1. Details of liver chemistry stopping criteria and required actions and follow-up assessments after liver stopping or monitoring event are given in Section 7 and [Appendix 7](#) All events of ALT $\geq 3 \times$ upper limit of normal (ULN) and bilirubin $\geq 2 \times$ ULN (>35% direct bilirubin) or ALT $\geq 3 \times$ ULN and international normalized ratio (INR) >1.5, if INR measured, which may indicate severe liver injury (possible Hy's Law), must be reported as an SAE (excluding studies of hepatic impairment or cirrhosis).
2. Blood for lipids (fasted) will be taken at pre-dose on day 1 and at day 21
3. Non-fasting sample except for pre-dose on day 1 and day 21.
4. Blood for INR and APTT will be taken at screening.

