2.2. Study Objective(s) and Endpoint(s)

Objectives	Endpoints
Primary Objectives	Primary Endpoints

 To evaluate the safety and tolerability of a single SC dose of GSK2330811 in healthy Japanese participants 	
 Number of participants reporting AEs. Number of participants reporting SAEs. Number of participants with vital signs (blood pressure, heart rate, body temperature) reaching a threshold of potential clinical importance Number of participants with treatment emergent abnormal ECG findings. Number of participants with CTCAE grade 1 or higher safety laboratory results (clinical chemistry, haematology values where CTCAE grading applies). Number of participants with treatment emergent abnormal urinalysis findings
Secondary Objectives	Secondary Endpoints

 To evaluate the pharmacokinetic (PK) profile of a single SC dose of GSK2330811 in healthy Japanese participants To assess the potential for anti-drug antibody formation following a single SC dose of GSK2330811 in healthy Japanese participants To assess effects of GSK2330811 on platelets and haemoglobin in healthy Japanese participants 	
 Pharmacokinetic parameters (Cmax, AUC, CL/F, Tmax, t_{1/2}, V_{ss}/F) Number of participants with anti-GSK2330811 antibodies Platelet nadir Time to platelet nadir Haemoglobin nadir Time to haemoglobin nadir
Exploratory Objectives	Exploratory Endpoints

 To explore the PD and the PK/PD relationship for GSK2330811 in the blood of healthy Japanese participants 	
 Serum levels of free OSM Serum levels of total OSM Levels of Thrombopoietin (TPO) Levels of Erythropoietin (EPO)

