4.2. Baseline Definitions

For all endpoints the baseline value will be the latest pre-dose assessment with a non-missing value, including those from unscheduled visits. If time is not collected, Day 1 (or Day -1 where applicable) assessments are assumed to be taken prior to first dose and used as baseline.

In case that triplicate assessments are performed, the mean of triplicate assessments at any given time point will be used as the value for that time point.

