4.2.1. Derivations and Handling of Missing Baseline Data

If baseline data is missing, no derivation will be performed, and baseline will be set to missing. The baseline definition will be footnoted on all change from baseline displays.

Definition	Reporting Details
Change from Baseline	= Post-Dose Visit – Baseline
% Change from Baseline	= $100 \times [(Post-Dose Visit – Baseline) / Baseline]$
Nadir	= Lowest post-baseline value of endpoint for a participant ^[1]
Time (Days) to Nadir	= Study Day of Nadir – 1 ^[1]

NOTES:

- 1: When there are multiple instances of the lowest value then the nadir used for reporting will be the earliest occurrence of that value.
- Unless otherwise specified, the baseline definitions specified in Section 4.2. Baseline Definitions will be used for derivations for endpoints / parameters and indicated on summaries and listings.
- Unless otherwise stated, if baseline data is missing no derivation will be performed and will be set to missing.
- The baseline definition will be footnoted on all change from baseline displays. 'Note: Baseline is defined as the pre-dose Day 1 assessment, unless unavailable, in which case it is the latest pre-dose assessment.'
- If there are multiple measurements (i.e. ECG) the derivation will be based on the average values where available.

CONFIDENTIAL

208564

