3.16.	Safety	SAFE_T4	Summary of Worst Case Urinalysis Results Post-Baseline Relative to Baseline	Tests to include: Urine blood, Urine Glucose (dipstick), Urine Ketones (dipstick), Urine Microscopy – Bacteria, Urine Microscopy - Red Blood Cells, Urine Microscopy - White Blood Cells, Urine Protein (dipstick), Urine Specific Gravity	SAC
ECG					
3.17.	Safety	EG1	Summary of ECG Findings		SAC
3.18.	Safety	EG2	Summary of ECG Values	Footnote: Average used for triplicate ECG measurements	SAC
3.19.	Safety	EG2	Summary of Change from Baseline in ECG Values	Footnote: Average used for triplicate ECG measurements	SAC
Vital Signs					
3.20.	Safety	VS1	Summary of Change from Baseline in Vital Signs		SAC
3.21.	Safety	VS7	Summary of Worst Case Vital Signs Results Relative to Potential Clinical Importance (PCI) Criteria Post-Baseline Relative to Baseline		SAC

CONFIDENTIAL

208564

Safety: Tables					
No.	Population	IDSL / Example Shell	Title	Programming Notes	Deliverable [Priority]
3.22.	Safety	SAFE_T5	Summary of Worst Case Vital Sign Results Relative to Change from Baseline Potential Clinical Importance (PCI) Criteria		SAC
Immunogenicity					
3.23.	Safety	IMM1	Occurrence of Anti-Drug Antibodies	Add footnote: Note: The denominator for confirmed positive is the total number of subjects at that visit who have immunogenicity data available.	SAC

CONFIDENTIAL

208564

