	Increase to 5-10	1 (<1%)		4 (2%)	
	Increase to 10-15	1 (<1%)		0	
	Increase to 15-20	2 (<1%)		1 (<1%)	

CONFIDENTIAL

208564

	Increase to 20-25	2 (<1%)	0
	Increase to 25-50	4 (2%)	1 (<1%)
W	n	230	232
	No Change/Decreased	222 (97%)	223 (96%)
	Any Increase	8 (3%)	9 (4%)
	Increase to NORMAL	6 (3%)	5 (2%)
	Increase to HIGH	6 (3%)	5 (2%)

Note: Little n does not include Not done or No results.

CONFIDENTIAL

208564

Example: SAFE_T5

Protocol: 208564

Population: Safety

Page 1 of n

Table 3.22
 Summary of Worst Case Vital Sign Results Relative to Change from Baseline Potential Clinical Importance (PCI) Criteria

Test (Unit)	Change Category	Placebo (N=XX)	GSK2330811 450 mg (N=XX)
Diastolic blood pressure (mmHg)	n	xx	xx
	Decrease >= 10	xx (xx%)	xx (xx%)
	Decrease >= 20	xx (xx%)	xx (xx%)
	Increase >= 10	xx (xx%)	xx (xx%)
	Increase >= 20	xx (xx%)	xx (xx%)
Heart Rate (bmp)	n	xx	xx
	Decrease >= 15	xx (xx%)	xx (xx%)
	Decrease >= 30	xx (xx%)	xx (xx%)
	Increase >= 15	xx (xx%)	xx (xx%)
	Increase >= 30	xx (xx%)	xx (xx%)
Systolic blood pressure (mmHg)	n	xx	xx
	Decrease >= 20	xx (xx%)	xx (xx%)
	Decrease >= 40	xx (xx%)	xx (xx%)
	Increase >= 20	xx (xx%)	xx (xx%)
	Increase >= 40	xx (xx%)	xx (xx%)

[figure not shown]
CONFIDENTIAL

208564

Example: SAFE_F1
 Protocol: 208564
 Population: Safety

Page 1 of n

Figure XX.XX
 Participant Profiles for Haematology by Treatment Group

Programming notes:

One legend including all participants.

Make plot as large as possible to fill space.

add (P) to denote placebo participants.

y-axis will be displayed on the left-hand side plot and the labels for the reference lines will be included on the right-hand side plot.

[figure not shown]
CONFIDENTIAL

208564

Example: SAFE_F2
 Protocol: 208564
 Population: Safety

Page 1 of n

Figure XX.XX
 Mean Profile for Haematology by Treatment Group

Programming notes:

See output 3.9 from 201247.

Make plot as large as possible to fill space.

Use different marker symbol, line pattern and colour by treatment group.

Table: Include N after treatment group and use same colour as in the plot.

[figure not shown]
CONFIDENTIAL

208564

Example: SAFE_F3
 Protocol: 208564
 Population: Safety

Page 1 of n

Figure XX.XX
 LTF Patient Profiles

Note: M = Male, F = Female, ALT = Alanine Amino Transferase, AST = Aspartate Amino Transferase, Alk. Phos. = Alkaline Phosphatase, Total Bili. = Total Bilirubin
 Clinical Concern Levels: ALT, AST and Alk. Phos: 2 times respective ULN, Total Bili: 1.5 times the ULN

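### The microscopy rows of SAP Table 3.16 omit new red-cell, white-cell and bacteria findings in participants who had no pre-dose urine microscopy

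*Protocol*

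**What the plan says.** - **When microscopy is done.** Protocol 10.2 (Appendix 2), Table 4, lists dipstick pH, glucose, protein, blood and ketones, and then "Microscopic examination (if blood or protein is abnormal").
- **Endpoint.** SAP 2.2 has as a primary endpoint "Number of participants with treatment emergent abnormal urinalysis findings".
- **Display.** SAP 12.9.5, Table 3.16, is the only urinalysis summary table. Its title is "Summary of Worst Case Urinalysis Results Post-Baseline Relative to Baseline". Three of its eight listed tests are microscopy: bacteria, and "Urine Microscopy - Red Blood Cells, Urine Microscopy - White Blood Cells".
- **Baseline.** SAP 4.2 says that "the baseline value will be the latest pre-dose assessment with a non-missing value, including those from unscheduled visits". Urinalysis is scheduled at screening and on Day -1.
- **Missing baseline.** SAP 4.2.1: "If baseline data is missing, no derivation will be performed, and baseline will be set to missing". Its notes repeat this as a default: "Unless otherwise stated, if baseline data is missing no derivation will be performed and will be set to missing". No exception is stated for microscopy.
- **Denominator.** Shell SAFE_T4 (SAP 12.10) carries the footnote "Note: Little n does not include Not done or No results". It names NONE SEEN as the lowest microscopy category but does not assign that value to a test that was not triggered.

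**The concern.** A reflex test and a shift-from-baseline table do not fit together. In healthy volunteers a clean dipstick before dosing is the ordinary case, and it means that microscopy was not required. If blood or protein later turns abnormal and microscopy then shows cells or bacteria, there is nothing to compare with, and the rules as written derive nothing.

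The selection works at both ends. A participant with pre-dose microscopy whose later dipsticks are all normal has no post-dose microscopy and also drops out. Under scheduled testing the rows hold only participants with an abnormal blood or protein dipstick both before and after dosing. They are the least informative group for a question about findings that emerge on treatment.

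At stake is how these rows will be read. White cells and bacteria have no dipstick counterpart in Table 4. New pyuria or bacteriuria would be in no laboratory summary table, although Protocol 2.3.1 lists infection as a potential risk. Near-empty rows could be taken as evidence that nothing new was seen.

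**Working it through.** The plan states no figure on this point, so there is none to reproduce. The check traces the rules through example participants and then gauges how thin the rows would be.

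**Tracing the rules.** Inputs are Protocol Table 4, SAP 4.2, SAP 4.2.1, Table 3.16 and shell SAFE_T4. The result categories are those in the shell.

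| Participant | Pre-dose | Post-dose | Dipstick row | Microscopy row |
|---|---|---|---|---|
| A | Blood and protein NEGATIVE throughout, no microscopy | Blood 1+, red cells 5-10 | Increase (blood) | Not derived |
| B | Blood and protein NEGATIVE throughout, no microscopy | Protein 1+, white cells and bacteria seen | Increase (protein) | Not derived |
| C | Blood 1+, red cells 0-1 | Blood 2+, red cells 5-10 | Increase (blood) | Increase (red cells) |
| D | Blood 1+, red cells 0-1 | All dipsticks normal, no microscopy | No increase | Not in n |

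A and B have the new findings and are absent from the microscopy rows. Both are still counted once in Table 3.16, through the dipstick row. For A, the number of participants with any increase in the table is 1 as the rules stand, and 1 if the microscopy result is also counted. For B, the dipstick row shows that protein rose, but no row shows the white cells or bacteria.

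**How many participants could have a microscopy baseline.** Let q be the probability that a participant has any pre-dose microscopy, triggered at screening or on Day -1. The documents give no value, so q = 5%, 10% and 20% are assumptions, with participants taken as independent. The expected number with a baseline is nq, and the probability that nobody has one is (1 − q)^n. The planned numbers are 7 active and 3 placebo (Protocol 4.2).

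| q | Expected of 7 active | P(none of 7) | Expected of 3 placebo | P(none of 3) | P(none of 10) |
|---|---|---|---|---|---|
| 5% | 0.35 | 0.95^7 = 70% | 0.15 | 0.95^3 = 86% | 0.95^10 = 60% |
| 10% | 0.70 | 0.90^7 = 48% | 0.30 | 0.90^3 = 73% | 0.90^10 = 35% |
| 20% | 1.40 | 0.80^7 = 21% | 0.60 | 0.80^3 = 51% | 0.80^10 = 11% |

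These figures count participants with a baseline. Appearing in a row also needs a post-dose microscopy, so the rows themselves can only be thinner.

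**The case against.** The strongest reply is that the endpoint counts participants, not microscopy results. After a clean baseline, scheduled microscopy happens only because dipstick blood or protein became abnormal. That change is itself an increase from NEGATIVE in the same table. This stands. A reader might infer that participants with new abnormalities vanish from the primary endpoint, and the documents do not support that. The narrow exception is microscopy ordered outside the reflex rule, which Protocol 10.2 permits through additional tests. With blood and protein negative and no baseline microscopy, such a result would show in no row of Table 3.16.

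Other safeguards stand in part:

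- Clinically significant urinalysis results are adverse events (Protocol 10.3.1) and reach the AE tables. Listing 23 shows all urinalysis results. Neither summarises microscopy findings that fall short of an adverse event.
- Microscopy triggered at screening can serve as baseline even if Day -1 is clean. So it would be wrong to say that a normal Day -1 dipstick always leaves no baseline. The rule can also mask a new finding, by comparing it with an earlier abnormal screening result.
- A programming note in SAFE_T4 asks programmers to alert the study team to character values that are neither the minimum nor shown as an increase category. At most this flags a dropped result. It does not say how to report it.
- SAP 12.3.1 classes assessments as treatment emergent by timing alone, but no urinalysis display is specified to use that rule.
- The sponsor's core data standards, which the laboratory displays follow, might treat a missing baseline differently. They are not in the documents, and the SAP text as it stands derives nothing.

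The trial is also descriptive and small, with no hypothesis test. That limits the consequence, but it does not make the rows informative.

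**Conclusion.** The point holds for the microscopy rows of Table 3.16. As written, they leave out new red-cell, white-cell and bacteria findings in every participant without pre-dose microscopy. Over the assumed trigger rates of 5% to 20%, the expected number of active participants with a baseline is 0.35 to 1.4, and the chance that there is none is 70% down to 21%.

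Two stronger readings are not supported. One is loss of the participant from the primary endpoint: the triggering dipstick change normally keeps him in the table. This assumes that an increase in any row makes a participant count, because the SAP does not say how the rows combine. The other is that empty rows are the expected result. That depends on a dipstick abnormality rate that the documents do not give; at the assumed rates, the chance that all 10 participants lack a baseline runs from 60% to 11%.

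The loss is of microscopy detail, chiefly white cells and bacteria, in the only summary table for a primary urinalysis endpoint. It is worth correcting because the correction is cheap.

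**What to change.** In SAP 4.2.1, exempt the urine microscopy tests from the missing-baseline rule. In Table 3.16 and shell SAFE_T4, for each microscopy test and treatment group, report:

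- the number of participants examined by microscopy after baseline;
- the number with any post-baseline result above NONE SEEN;
- that number split into participants with baseline microscopy (shift shown) and participants in whom it was not triggered (no shift).

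Setting every untriggered baseline to NONE SEEN is less sound. Negative dipstick blood and protein say little about white cells or bacteria, and filling in untested visits would put people who were never examined into the denominator. If imputation is preferred, limit it to red cells where baseline dipstick blood was negative, and footnote how many baselines were set this way.

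The cost is a short SAP addition, a revised shell and a programming rule, with no extra samples or visits. The downside is that where baseline was not examined, a finding counted after dosing may have been there before. The split discloses this.

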10.3.1. Definition of AE

AE Definition

- An AE is any untoward medical occurrence in a clinical study participant, temporally associated with the use of a study intervention, whether or not considered related to the study intervention.
- NOTE: An AE can therefore be any unfavorable and unintended sign (including an abnormal laboratory finding), symptom, or disease (new or exacerbated) temporally associated with the use of a study intervention.

Events Meeting the AE Definition

- Any abnormal laboratory test results (haematology, clinical chemistry, or urinalysis) or other safety assessments (e.g., ECG, radiological scans, vital signs measurements), including those that worsen from baseline, considered clinically significant in the medical and scientific judgment of the investigator (i.e., not related to progression of underlying disease).
- Exacerbation of a chronic or intermittent pre-existing condition including either an increase in frequency and/or intensity of the condition.
- New conditions detected or diagnosed after study intervention administration even though it may have been present before the start of the study.
- Signs, symptoms, or the clinical sequelae of a suspected drug-drug interaction.
- Signs, symptoms, or the clinical sequelae of a suspected overdose of either study intervention or a concomitant medication. Overdose per se will not be reported as an AE/SAE unless it is an intentional overdose taken with possible suicidal/self-harming intent. Such overdoses should be reported regardless of sequelae.

Events NOT Meeting the AE Definition

- Any clinically significant abnormal laboratory findings or other abnormal safety assessments which are associated with the underlying disease, unless judged by the investigator to be more severe than expected for the participant's condition.
- The disease/disorder being studied or expected progression, signs, or symptoms of the disease/disorder being studied, unless more severe than expected for the participant's condition.
- Medical or surgical procedure (e.g., endoscopy, appendectomy): the condition that leads to the procedure is the AE.

- Situations in which an untoward medical occurrence did not occur (social and/or convenience admission to a hospital).
- Anticipated day-to-day fluctuations of pre-existing disease(s) or condition(s) present or detected at the start of the study that do not worsen.

10.3.2. Definition of SAE

If an event is not an AE per definition above, then it cannot be an SAE even if serious conditions are met (e.g., hospitalization for signs/symptoms of the disease under study, death due to progression of disease).

A SAE is defined as any untoward medical occurrence that, at any dose:

- Results in death
- Is life-threatening

The term 'life-threatening' in the definition of 'serious' refers to an event in which the participant was at risk of death at the time of the event. It does not refer to an event, which hypothetically might have caused death, if it were more severe.

Requires inpatient hospitalization or prolongation of existing hospitalization

- In general, hospitalization signifies that the participant has been detained (usually involving at least an overnight stay) at the hospital or emergency ward for observation and/or treatment that would not have been appropriate in the physician's office or outpatient setting. Complications that occur during hospitalization are AE. If a complication prolongs hospitalization or fulfills any other serious criteria, the event is serious. When in doubt as to whether "hospitalization" occurred or was necessary, the AE should be considered serious.
- Hospitalization for elective treatment of a pre-existing condition that did not worsen from baseline is not considered an AE.

Results in persistent or significant disability/incapacity

- The term disability means a substantial disruption of a person's ability to conduct normal life functions.
- This definition is not intended to include experiences of relatively minor medical significance such as uncomplicated headache, nausea, vomiting, diarrhea, influenza, and accidental trauma (e.g. sprained ankle) which may interfere with or prevent everyday life functions but do not constitute a substantial disruption.

Is a congenital anomaly/birth defect

Other situations:

- Medical or scientific judgment should be exercised in deciding whether SAE reporting is appropriate in other situations such as important medical events that may

not be immediately life-threatening or result in death or hospitalization but may jeopardize the participant or may require medical or surgical intervention to prevent one of the other outcomes listed in the above definition. These events should usually be considered serious.

- Examples of such events include invasive or malignant cancers, intensive treatment in an emergency room or at home for allergic bronchospasm, blood dyscrasias or convulsions that do not result in hospitalization, or development of drug dependency or drug abuse.

10.3.3. Recording and Follow-Up of AE and SAE

AE and SAE Recording

- When an AE/SAE occurs, it is the responsibility of the investigator to review all documentation (e.g. hospital progress notes, laboratory, and diagnostics reports) related to the event.
- The investigator will then record all relevant AE/SAE information in the CRF.
- It is **not** acceptable for the investigator to send photocopies of the participant's medical records to GSK in lieu of completion of the GSK /AE/SAE CRF page.
- There may be instances when copies of medical records for certain cases are requested by GSK. In this case, all participant identifiers, with the exception of the participant number, will be redacted on the copies of the medical records before submission to GSK.
- The investigator will attempt to establish a diagnosis of the event based on signs, symptoms, and/or other clinical information. Whenever possible, the diagnosis (not the individual signs/symptoms) will be documented as the AE/SAE.

Assessment of Intensity

The investigator will make an assessment of intensity for each AE and SAE reported during the study and assign it to 1 of the following categories:

- **Mild:** An event that is easily tolerated by the participant, causing minimal discomfort and not interfering with everyday activities.
- **Moderate:** An event that causes sufficient discomfort and interferes with normal everyday activities.
- **Severe:** An event that prevents normal everyday activities. An AE that is assessed as severe should not be confused with an SAE. Severe is a category utilized for rating the intensity of an event; and both AE and SAE can be assessed as severe.

An event is defined as 'serious' when it meets at least 1 of the predefined outcomes as described in the definition of an SAE, NOT when it is rated as severe.

Assessment of Causality

- The investigator is obligated to assess the relationship between study intervention and each occurrence of each AE/SAE.
- A "reasonable possibility" of a relationship conveys that there are facts, evidence, and/or arguments to suggest a causal relationship, rather than a relationship cannot be ruled out.
- The investigator will use clinical judgment to determine the relationship.
- Alternative causes, such as underlying disease(s), concomitant therapy, and other risk factors, as well as the temporal relationship of the event to study intervention administration will be considered and investigated.
- The investigator will also consult the Investigator's Brochure (IB) and/or Product Information, for marketed products, in his/her assessment.
- For each AE/SAE, the investigator **must** document in the medical notes that he/she has reviewed the AE/SAE and has provided an assessment of causality.
- There may be situations in which an SAE has occurred, and the investigator has minimal information to include in the initial report to GSK. However, **it is very important that the investigator always make an assessment of causality for every event before the initial transmission of the SAE data to GSK.**
- The investigator may change his/her opinion of causality in light of follow-up information and send an SAE follow-up report with the updated causality assessment.
- The causality assessment is one of the criteria used when determining regulatory reporting requirements.

Follow-up of AE and SAE

- The investigator is obligated to perform or arrange for the conduct of supplemental measurements and/or evaluations as medically indicated or as requested by GSK to elucidate the nature and/or causality of the AE or SAE as fully as possible. This may include additional laboratory tests or investigations, histopathological examinations, or consultation with other health care professionals.
- If a participant dies during participation in the study or during a recognized follow-up period, the investigator will provide GSK with a copy of any post-mortem findings including histopathology.
- New or updated information will be recorded in the originally completed CRF.
- The investigator will submit any updated SAE data to GSK within 24 hours of receipt of the information.

